**Table 10: Example for 'Return to Usual Health' question**

	ARI Day 1 - Onset (11/11/2019)	ARI Day 2 (12/11/2019)	ARI Day 3 (13/11/2019)	ARI Day 4 (14/11/2019)	ARI Day 5 (15/11/2019)	ARI Day 6 (16/11/2019)	ARI Day 7 (17/11/2019)	ARI Day 8 (18/11/2019)
Participant 1	No	No	Yes	No	Yes	Yes	Yes	Yes
Participant 2	No	No	Yes	Yes	Yes	No	No	No

Note: in case a participant has two or more different responses at the same day, then the 'No' answer will be taken into account for calculating the number of days a participant took to return to his usual health.

#### 4.5.2.1. Analysis Methods

Patient global impression scores will be analyzed based on the PPE set, with a major focus participants with any RT-PCR disease (see [above](#) for definition).

For the PGI-H, number of observations, mean, standard error, median, first and third quartile, minimum and maximum will be tabulated and means with standard errors will be graphically presented per group and time point for the change from baseline.

For the PGI-C and PGI-S scores, score, number of observations, mean, standard error, median, first and third quartile, minimum and maximum will be tabulated and means with standard errors will be graphically presented per group and time point.

For the PGI-H, descriptive statistics of the baseline, the end of season and the change between these two timepoints will be calculated for all participants based on the PPE set, for participants with any RT-PCR-confirmed RSV disease and for participants meeting each of the primary endpoints separately, based on the PPE set.

The number (and percentage) of participants answering yes and no in the 'Return to Usual Health' question will be calculated per day.

Moreover, the number of days a participant took to return to its usual health will be summarized and graphically presented with Kaplan Meir curves.

In case two or more assessments are reported at the same day (for example eDiary and eDevice or two assessments at the same device) then the worst PGI score (or when looking to Return to Usual Health, the worst answer to this question) will be used.

In case a participant experiences two or more ARIs during the study the same rule as for the RiiQ will be used.

Note 1: For outputs where only planned visits (ARI Day 3-5, ARI Day 29, End of season) are presented, the worst across the different scheduled and unscheduled visits will be presented per visit.

## 4.6. Lawton-Brody Instrumental Activities of Daily Living (IADL) Scale

The Lawton-Brody IADL questionnaire covers 8 domains (see [Attachment 7](#)). Women are scored on all 8 domains; for men, the domains of food preparation, housekeeping, and laundering are excluded from the analysis, regardless if they are filled in. Participants are scored according to their highest level of functioning in that category (either 0 or 1). A summary score ranges from 0 (low function, dependent) to 8 (high function, independent) for women, and from 0 through 5 for men.

### 4.6.1. Analysis Methods

For all participants with any RT-PCR-confirmed RSV disease (see [above](#) for definition) from the PPE set, descriptive statistics of the actual values and the change from baseline of the IADL score will be tabulated by sex and group for each timepoint collected.

In case two or more assessments are reported at the same day then the worst total Lawton Brody score will be used. The worst score is the smallest.

In case a participant experiences two or more ARIs during the study the same rule as for the RiiQ will be used.

Note: For outputs were only planned visits (ARI Day 3-5, ARI Day 29, End of season) are presented, the worst across the different scheduled and unscheduled visits will be presented per visit.

## 4.7. Frailty Index Score

The frailty index score will be calculated from the medical conditions of interest (CETERM, see Section 4.1.5.1) and the Lawton-Brody IADL questionnaire, based on the following equations:

*Frailty Index for women*

$$= \frac{25}{33} * \left( \frac{\# \text{ of medical conditions the participant has}}{25} \right) + \frac{8}{33} * \left( 1 - \frac{\text{Lawton Brody IADL score}}{8} \right)$$

*Frailty Index for men*

$$= \frac{25}{30} * \left( \frac{\# \text{ of medical conditions the participant has}}{25} \right) + \frac{5}{30} * \left( 1 - \frac{\text{Lawton Brody IADL score}}{5} \right)$$

The range of the frailty index score will be between 0 and 1, with 0 indicating that the participants is not frail and 1 indicating that the participant is most frail.

Moreover, an additional frailty index augmented with the RiiQ data will also be calculated, based on the following equations:

**Frailty Index augmented for women**

$$= \frac{25}{34 + N} \left( \frac{\# \text{ of medical conditions the participant has}}{25} \right) + \frac{8}{34 + N} \left( 1 - \frac{\text{score of Lawton}}{8} \right) \\ + \frac{N}{34 + N} \left( \frac{\# \text{ of RiiQ symptoms/activities the participant has}}{N} \right)$$

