##### 4.1.5.1. Medical Conditions of Interest

The following medical conditions are of interest:

Categories	Medical Conditions of Interest
Endocrine	Diabetes mellitus
Liver illness	Hepatic cirrhosis
Cancer	Non-malignant tumor
Cardiac illness	Angina
	Arrhythmia
	Valvular (prosthetic aortic or mitral valves)
	Myocardial infarction
	Congestive heart failure (CHF)
Vascular illness	Peripheral vascular
	Hyperlipidemia
	Hypertension
	Cerebrovascular (stroke, transient ischemic attack)
Pulmonary illness	Asthma
	COPD
Renal illness	Chronic renal failure
	Nephrotic syndrome
Neuro-Muscular illness	Seizure disorder
	Spinal cord injury
	Parkinson's
Gastrointestinal illness	Inflammatory bowel disease (Crohn's, ulcerative colitis)
	Peptic ulcer
	Gastroesophageal reflux disease
Mental Health Diagnoses	Depression
	Anxiety
	Bipolar mood disorder

These medical conditions of interest will be tabulated per category and group.

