**Frailty Index augmented for men**

$$= \frac{25}{30 + N} * \left( \frac{\# \text{ of medical conditions the participant has}}{25} \right) + \frac{5}{30 + N} * \left( 1 - \frac{\text{score of Lawton}}{5} \right) \\ + \frac{N}{30 + N} \left( \frac{\# \text{ of RiiQ symptoms/activities the participant has}}{N} \right), \text{ for men}$$

where  $N = N_1 + N_2 + N_3 + N_4$  (see below).

**Note:** For the end of season the medical conditions from baseline are used.

The frailty index will only be calculated for participants that have completed all assessments required for the calculation of the index.

The augmented frailty index will only be calculated for participants that have completed medical conditions of interest, the Lawton Broady, and more than 50% of the RiiQ items required for the calculation of the index (where  $N \geq 13$ ).

For calculating the number of RiiQ symptoms/activities the subject has, the following rules will be followed:

- Each one of the assessed RiiQ Respiratory and Systemic symptoms of any grade will count as one symptom ( $N_1$ =total number of non-missing symptoms/activities, maximum number 13)
- Each one of the assessed RiiQ Impact on Daily Activities with a severity of ‘moderate’ or ‘great difficulty’ will count as one ( $N_2$ =total number of non-missing symptoms/activities, maximum number 7)
- If one of the questions in the RiiQ Impact on Emotions scale has a response of ‘moderate’ or ‘extremely’ then it will be counted as just one symptom (regardless if all 4 questions have a ‘moderate’ or ‘extremely’ response) ( $N_3 = 1$ , if 1 or more questions with a response of ‘moderate’ or ‘extremely’, or 0 otherwise)
- Each one of the following RiiQ Impact on Relationships questions has a response of ‘moderate concerned’ or ‘extremely concerned’ will count as one ( $N_4$ =total number of non-missing symptoms/activities, maximum number 4):
  1. ‘People worrying about you’
  2. ‘Being a burden’
  3. ‘People wing annoyed with you’
  4. ‘Needing to depend on people’ or ‘People having to do extra things for you’

**Note:** For end of season frailty calculation, in case two or more assessments are reported at the same day or more than one visit is completed (scheduled and unscheduled visits) then the same rules as in Sections 4.5.1.1 and 4.6.1 will be applied,

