#### **4.13. Connection between Primary Endpoint and Patient reported Measures, clinical assessment and frailty index**

In order to establish the interrelationship between the primary endpoints and PROs, the following analyses will be performed restricted to the placebo group. These analyses will be performed on two subgroups of the PPE set:

- participants with any RT-PCR confirmed RSV disease (see [above](#) for definition)
- participants with any ARI (see [Any ARI](#) definition, independently of RSV etiology)

For the following patient reported measures:

- AUC of the change from baseline for the Total RiiQ Respiratory and Systemic symptom score
- AUC of the change from baseline for the Total RiiQ Case Definition symptom score
- AUC of the change from baseline for the Total RiiQ Impact on Daily Activity score
- The change in IADL score between ARI Day 3-5 and baseline
- The change in augmented frailty score between baseline and end of season

The number of observations, median, first and third quartile, will be calculated for participants meeting each case definition and participants not meeting any case definition or not meeting the considered case definition; this will also be graphically depicted with boxplots.

Note: In case a participant experiences two or more ARIs during the study the same rule as for the RiiQ will be used.

As a sensitivity check the same analysis will be performed but without taking into account cough for any of the case definitions.

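### Section 4.7 contains two separate scoring errors in the augmented frailty index: the women's formula divides by 34 + N instead of 33 + N, and in both sexes the emotion item enters N only when the deficit is present.

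*SAP*

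**What the plan says.** SAP Section 4.7 defines a basic frailty index from the medical conditions of interest and the Lawton-Brody score, with denominators of 33 for women and 30 for men. It then defines an index augmented with RiiQ data.

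- Under "Frailty Index augmented for women", the numerator weights are 25, 8 and N, and all three terms are divided by 34 + N.
- Under "Frailty Index augmented for men", the numerator weights are 25, 5 and N, and all three terms are divided by 30 + N.
- A single definition, N = N1 + N2 + N3 + N4, serves both sexes. N1 (symptoms, up to 13), N2 (daily activities, up to 7) and N4 (relationships, up to 4) count non-missing items. N3 (emotions) is set to 1 "if 1 or more questions with a response of ‘moderate’ or ‘extremely’, or 0 otherwise".
- The augmented index is calculated only where N is at least 13.

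Section 4.7.1 summarises the augmented index at baseline and end of season and its change, and plots it against the basic index. Section 4.13 lists "The change in augmented frailty score between baseline and end of season" among the measures compared by case definition in the placebo group. Neither section specifies a split by sex, whereas Section 4.6.1 does tabulate the Lawton-Brody score by sex.

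**The concern.** A deficit index is the number of deficits present divided by the number of items considered, so its weights should sum to 1. In the augmented women's formula they do not, although in the men's formula and in both basic formulas they do. Women and men therefore sit on slightly different scales in outputs that combine them.

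The N3 rule raises a different problem, common to both sexes. For the other RiiQ components, an item that was assessed and found absent stays in the denominator. For the emotion item, the answer itself decides whether the item is in the denominator. The change from baseline, and sometimes eligibility for the index, then depend on the response rather than on what was assessed. A programmer who follows the text will reproduce both errors.

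**Working it through.** **Inputs**

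- Conditions: Section 4.1.5.1 introduces its table with "The following medical conditions are of interest". Counting entries by category gives 1+1+1+5+4+2+2+3+3+3 = 25.
- Lawton-Brody maximum: Section 4.6 states "A summary score ranges from 0 (low function, dependent) to 8 (high function, independent) for women, and from 0 through 5 for men", so 8 and 5.
- RiiQ items: 13 + 7 + 4 = 24 without the emotion item and 25 with it. The lower limit is N = 13 (13/25 = 52%).

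**Step 1: basic index.** The maximum is the sum of the weights. Women: (25+8)/33 = 1. Men: (25+5)/30 = 1. This agrees with the 0 to 1 range that Section 4.7 gives for the basic index.

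**Step 2: augmented index, maximum.**

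| N | Women as written, (33+N)/(34+N) | Women with 33 + N | Men, (30+N)/(30+N) |
|---|---|---|---|
| 13 | 46/47 = 0.979 | 1.000 | 1.000 |
| 24 | 57/58 = 0.983 | 1.000 | 1.000 |
| 25 | 58/59 = 0.983 | 1.000 | 1.000 |

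The same ratio multiplies every woman's score, so the shortfall is 1/59 = 1.7% (N = 25) to 1/47 = 2.1% (N = 13). For a woman with 10 deficits at N = 24, this is 10/58 = 0.172 instead of 10/57 = 0.175.

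**Step 3: the N3 rule and change from baseline.** Let M be the denominator at baseline with the emotion deficit absent, and d the number of deficits. If the emotion deficit then appears and nothing else changes:

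- as written, the change is (d+1)/(M+1) − d/M = [1/(M+1)] × (1 − d/M);
- with the item counted at both visits, the change is 1/(M+1).

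The contribution is understated by the fraction d/M. With d = 10 and all other RiiQ items assessed:

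- Men (M = 54): 11/55 − 10/54 = 0.0148 instead of 1/55 = 0.0182, a shortfall of 10/54 = 18.5%.
- Women with the printed 34 + N (M = 58): 11/59 − 10/58 = 0.0140 instead of 1/59 = 0.0169, a shortfall of 10/58 = 17%.

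**Step 4: the N3 rule and eligibility.** Take a participant with 12 other RiiQ items assessed and the emotion scale answered. If the emotion deficit is absent, N = 12 and no index is calculated. If it is present, N = 13 and the index is calculated. An unanswered emotion scale also gives N3 = 0, so it cannot be told apart from an absent deficit.

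**Step 5: are the two errors linked?** Under the N3 rule as written, a participant with every deficit except emotion scores 54/54 = 1 (men) or, with 33 + N, 57/57 = 1 (women). The N3 rule therefore does not prevent a score of 1. It also applies the same N to both sexes. The women's ceiling and the scale difference from men come only from 34 in place of 33.

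**The case against.** The strongest case against giving this weight is its size and reach. The denominator error moves a typical woman's score by about 0.003 (10/57 − 10/58). With the N3 rule kept as it is, it moves the one-deficit change by only 0.0002 (11/58 − 10/57 = 0.0142 against 0.0140). The scale factor depends on sex and N, not on vaccine group. The augmented index feeds only descriptive statistics and plots in Sections 4.7.1 and 4.13, and Section 5.12 does not carry it into later seasons. All of this stands, and it limits the point to a minor one.

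It is also fair to say that N1, N2 and N4 count non-missing items by design, so N can differ between visits even after the correction. That stands too: the fix removes a denominator driven by the response, but does not make N constant.

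It cannot be argued that the extra 1 in 34 stands for the emotion item. N already contains N3, and the men's formula would then need 31 + N. The figure appears in all three terms, so a slip in reading the PDF is unlikely.

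A reader might infer three stronger things that the document does not support:

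- *That the N3 rule causes the women's ceiling or the difference from men.* Step 5 shows it causes neither.
- *That the formula contradicts a stated range.* The 0 to 1 range is given for the basic index and is not restated for the augmented one.
- *That the frailty categories are wrong.* Section 4.7.1 defines them for the basic index, whose weights are correct, and the baseline frailty subgroups in Section 2.4 use the same cut-points.

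**Conclusion.** Both errors hold, as separate points. The women's augmented index is 1.7% to 2.1% too low and peaks at 0.979 to 0.983, while the men's can reach 1. In both sexes, the N3 rule makes the denominator and the N ≥ 13 requirement depend on the emotion response, and it under-weights a newly appearing emotion deficit by the fraction d/M (17% to 18.5% in the examples).

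The first result needs only the SAP's own item counts. The second rests on reading the N3 definition literally. The size of the example also assumes 10 baseline deficits, all other RiiQ items assessed at both visits, and no other change.

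The impact is minor. The errors are confined to descriptive, exploratory outputs of the augmented index. The basic index, its categories and the efficacy analyses are untouched.

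**What to change.** - **Women:** in Section 4.7, replace 34 + N with 33 + N in all three terms of the augmented formula.
- **Both sexes:** set N3 = 1 whenever the emotion scale was answered, with the response deciding only whether the deficit counts in the numerator. A participant with every deficit except emotion would then score 57/58 = 0.983 (women) or 54/55 = 0.982 (men), instead of 1. An unanswered scale would give N3 = 0 and be distinct from an absent deficit.
- **Programs:** check what the first-season program used. If it followed this text, rerun the augmented-index outputs of Sections 4.7.1 and 4.13.

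The cost is a formula correction, one rule rewritten, a program check and possibly a rerun of a few descriptive tables and plots. No new data are needed.

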**Frailty Index augmented for men**

$$= \frac{25}{30 + N} * \left( \frac{\# \text{ of medical conditions the participant has}}{25} \right) + \frac{5}{30 + N} * \left( 1 - \frac{\text{score of Lawton}}{5} \right) \\ + \frac{N}{30 + N} \left( \frac{\# \text{ of RiiQ symptoms/activities the participant has}}{N} \right), \text{ for men}$$

where  $N = N_1 + N_2 + N_3 + N_4$  (see below).

**Note:** For the end of season the medical conditions from baseline are used.

The frailty index will only be calculated for participants that have completed all assessments required for the calculation of the index.

The augmented frailty index will only be calculated for participants that have completed medical conditions of interest, the Lawton Broady, and more than 50% of the RiiQ items required for the calculation of the index (where  $N \geq 13$ ).

For calculating the number of RiiQ symptoms/activities the subject has, the following rules will be followed:

- Each one of the assessed RiiQ Respiratory and Systemic symptoms of any grade will count as one symptom ( $N_1$ =total number of non-missing symptoms/activities, maximum number 13)
- Each one of the assessed RiiQ Impact on Daily Activities with a severity of ‘moderate’ or ‘great difficulty’ will count as one ( $N_2$ =total number of non-missing symptoms/activities, maximum number 7)
- If one of the questions in the RiiQ Impact on Emotions scale has a response of ‘moderate’ or ‘extremely’ then it will be counted as just one symptom (regardless if all 4 questions have a ‘moderate’ or ‘extremely’ response) ( $N_3 = 1$ , if 1 or more questions with a response of ‘moderate’ or ‘extremely’, or 0 otherwise)
- Each one of the following RiiQ Impact on Relationships questions has a response of ‘moderate concerned’ or ‘extremely concerned’ will count as one ( $N_4$ =total number of non-missing symptoms/activities, maximum number 4):
  1. ‘People worrying about you’
  2. ‘Being a burden’
  3. ‘People wing annoyed with you’
  4. ‘Needing to depend on people’ or ‘People having to do extra things for you’

**Note:** For end of season frailty calculation, in case two or more assessments are reported at the same day or more than one visit is completed (scheduled and unscheduled visits) then the same rules as in Sections 4.5.1.1 and 4.6.1 will be applied,

#### 4.7.1. Analysis Methods

For both the frailty index and the frailty index augmented with the RiiQ, descriptive statistics of the baseline, the end of season and the change between these two timepoints will be calculated for all participants based on the PPE set, for participants with any RT-PCR-confirmed RSV disease and for participants fulfilling each case definition separately, based on the PPE set.

For the frailty index the following categories will be defined and the number of subjects moving to a different category after the end of the RSV season will be tabulated and graphically presented:

- 0-0.1: not frail
- 0.11-0.2: pre-frail
- 0.21-0.45: frail
- >0.45: most frail

For subjects with any RT-PCR-confirmed RSV disease from the PPE set, the correlation of the baseline frailty index with the total RiiQ scores and with the duration of the ARI episode will be explored with scatterplots.

Finally, the correlation between the two indexes will be explored with scatterplots.

#### 4.8. Clinical Assessment

The clinical assessment consists of 4 different sub-assessments [vital signs, physical examination scoring, upper respiratory and lower respiratory]. Based on the physical examination scoring, upper respiratory and lower respiratory assessments the following total scores will be calculated:

- **Total symptom scores assessed during the clinical assessment** is calculated as the mean of all 4 systemic symptom (cough, sputum levels, Shortness of breath, Malaise (tiredness)).
- **Total upper respiratory score assessed during the clinical assessment** is calculated as the mean of all 3 upper respiratory levels (Nasal Discharge, Pharyngitis and Sinus Tenderness).
- **Total lower respiratory score assessed during the clinical assessment** is calculated as the mean of all 4 lower respiratory levels (Dyspnea, Wheezing, Respiratory Effort and Rales, rhonchi or other).

**Note:** Total scores will be calculated based on the number of assessments completed by the participant and in cases where more than 50% of data needed for a score is not collected (reported as ‘Not done’), then the value for that score will be set to missing. For example, if a participant has responded to 2 or 3 out of the 4 systemic score questions the ‘Total symptom scores assessed during the clinical assessment’ score will be the mean of the 2 or 3 available questions, respectively. If the participant has only completed 1 of the questions, then the score will be set to missing.

#### 4.8.1. Analysis Methods

The clinical assessment will be analyzed based on the PPE set, with a major focus participants with any RT-PCR disease (see [above](#) for definition) .

For the **total scores**, descriptive statistics will be tabulated per group and time point for the actual values and the change from baseline and means with standard errors will be graphically presented per group and time point for the change from baseline alone.

For **vital signs** from the clinical assessments questionnaire apart from oxygen saturation, abnormalities emerging after vaccination will be tabulated by worst abnormality grade using [Table 11](#), per timepoint collected. An abnormality will be considered as emerging in a particular period if it is worse than the baseline value. If the baseline is missing, the abnormality is always considered emerging. Cross tabulation of the emerging worst grades of vital signs versus the status at reference will be calculated.

**Table 11: Vital Signs Toxicity Grading**

Vital Signs	Mild (Grade 1)	Moderate (Grade 2)	Severe (Grade 3)	Potentially Life-threatening (Grade 4)
Fever (°C)	38.0 – 38.4	38.5 – 38.9	39.0 – 40	>40
Fever (°F)	100.4 – 101.1	101.2 – 102.0	102.1 – 104	>104
Tachycardia - beats per minute	101 – 115	116 – 130	>130	Hospitalization for arrhythmia
Bradycardia - beats per minute	50 – 54	45 – 49	<45	Hospitalization for arrhythmia
Hypertension (systolic) - mm Hg	141 – 150	151 – 160	>160	Hospitalization for malignant hypertension
Hypertension (diastolic) - mm Hg	91 – 95	96 – 100	>100	Hospitalization for malignant hypertension
Hypotension (systolic) – mm Hg	85 – 89	80 – 84	<80	Hospitalization for hypotensive shock
Respiratory Rate – breaths per minute	17 – 20	21 – 25	>25	Intubation

For the determination of oxygen saturation, the number of participants (and percentages) with baseline SpO2 ≥90% and SpO2 <90% during the ARI episode, the number of participants (and percentages) with baseline SpO2 <90 and that have a ≥3% decrease during ARI episode and the number of participants (and percentages) with missing baseline and SpO2 <90% during the ARI episode will be tabulated per group.

For symptoms assessed at ARI Day 3-5 both by the site staff on the clinical assessment and by the participant on the RiiQ, tetrachoric and polychoric correlations for the presence and severity, respectively will be calculated, pooling both groups together. Moreover, the correlation between the different RiiQ symptoms collected at the ARI day with most symptoms reported, may be calculated and visualized with a heatmap. Similarly, the correlation between the different clinical assessment symptoms at ARI Day 3-5 may also be explored.

In case two or more assessments are reported at the same day (for example two assessments at the same device) then the worst total score per assessment and the worst vital sign grade per symptom will be used.

In case a participant experiences two or more ARIs (based on the ‘Any ARI’ definition, Section 4.4.3.1) during the study then the following rules will be followed in identifying which ARIs data will be used:

- If all fulfil a case definition, then data from the RT-PCR confirmed RSV disease fulfilling the strictest definition will be used (case definition 1 > case definition 2 > case definition 3)
- If only one fulfils a case definition, then those data will be used
- If none fulfils a case definition or all fulfil the same case definition, then data from the first RT-PCR confirmed RSV disease will be used.
- If none is a RT-PCR confirmed RSV-disease, then use:
  - the ARI that fulfils the strictest case definition based on symptoms only (case definition 1 > case definition 2 > case definition 3) Or
  - the first ARI, in case 2 or more fulfil the same case definition on symptoms only or in case they do not fulfil any case definition on symptoms only.

Note: For outputs were only planned visits (ARI Day 3-5, ARI Day 29, End of season) are presented, the worst across the different scheduled and unscheduled visits will be presented per visit.

